5.5 Premature Discontinuation of the Intervention

A study subject can discontinue the study intervention (low-dose 5-FC) in the event of any of the following:

- Any clinical adverse event (AE), laboratory abnormality, concurrent illness, or other medical condition or situation occurs such that continued participation with an intervention would not be in the best interest of the subject
- Decompensation of the cryptococcal meningitis
- Subject wishes to voluntarily discontinue therapy

Subjects are free to discontinue an intervention at any time upon request or in the opinion of the investigator in the event of decompensation and disease progression. Examples of progression would be development of altered mental status, increasing CSF quantitative culture CFU counts by >1 log₁₀ CFU/mL, other medical events leading to an inability to take oral medicines, etc.

Subjects discontinuing low-dose 5-FC would then be given standard dose 5-FC, as clinically necessary.

Every effort will be made to undertake protocol-specific study procedures. If voluntary discontinuation occurs, the subject will be asked to continue scheduled evaluations, complete an end-of-study evaluation, and be given appropriate care under medical supervision until the symptoms of any AE resolve or the subject's condition becomes stable. The patient will be offered ongoing follow-up care at the site outpatient HIV clinic or referred to a clinic of their choice if withdrawn from the study.

Alterations in dose will be considered a protocol deviation, since the goal of the trial is to assess the effect of dose-reduction. Patients may remain in the study but dose-adjustments will be documented and reported to the IRB.

Subjects discontinuing the intervention will receive standard of care therapy through 18 weeks.

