6.2.1.1 Amphotericin B Deoxycholate

Amphotericin B deoxycholate is available in single vials. Each vial contains a sterile, non-pyrogenic, lyophilized cake providing 50 mg amphotericin B and 41 mg sodium deoxycholate buffered with sodium phosphates. Amphotericin B is solubilized by the addition of sodium deoxycholate to form a mixture, which provides a colloidal dispersion for intravenous infusion following reconstitution.

Typical AMB deoxycholate dosing for CM is 0.7-1 mg/kg daily. Amphotericin should be administered by slow intravenous infusion over a period of approximately 4 hours. The recommended concentration for intravenous infusion is 0.1 mg/mL (1 mg/10 mL).

Acquisition: Any nationally registered, GMP-manufactured, and/or FDA-approved formulation is acceptable.

Product Storage and Stability: Prior to reconstitution, AMB deoxycholate should be stored under refrigeration 2° to 8°C (36° to 46°F) and protected against exposure to light.

Study administration for all treatment arms:

Subjects will receive the WHO standard 7-day course of IV amphotericin B deoxycholate 0.7-1.0mg/kg/day.

Amphotericin is well known for its frequent and often severe side effects, as outlined in Appendix A. Significant infusion reactions must be anticipated with a tendency toward IV-associated phlebitis. To help prevent this, IV lines will be flushed after amphotericin is administered and peripheral IV sites generally rotated at least every 3 days. With IV AMB, provide 1–2 L saline/day, along with careful monitoring for renal dysfunction and particularly electrolyte abnormalities (K and Mg). Electrolyte management with amphotericin is essential, and will follow WHO treatment guidelines including supplemental potassium and magnesium.⁵³

Guidelines for use of IV AMB and management of common toxicities associated with amphotericin B are included in the MOP and may be consulted, at the site investigator's discretion. Participants who permanently and prematurely discontinue IV AMB because of an AE will be followed closely until resolution of the AE can be documented. Those who require additional IV AMB in any arm will be tracked, as additional IV AMB is a secondary endpoint.

When not receiving IV AMB, additional IV fluids will be given as clinically indicated.

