9.1 Adverse Event (AE) Definitions

The intervention during this trial is the reduced dose of flucytosine for induction therapy.

Adverse Event (AE)

An AE is any untoward medical occurrence in a clinical investigation subject administered a pharmaceutical product and which does not necessarily have to have a causal relationship with this treatment. An AE can therefore be any unfavorable or unintended sign (including abnormal laboratory findings), symptom, or disease temporally associated with the use of a medicinal product. Any symptom, sign, illness or experience that develops or worsens in severity during the course of the study are considered AEs.

Any medical condition already present at the time of screening should not be reported as an adverse event unless the medical condition or signs or symptoms present at baseline changes in severity or seriousness at any time during the study. In this case, it should be reported as an adverse event.

As a diagnosis may have multiple signs or symptoms associated with the AE (e.g., sepsis presenting with fever, hypotension, confusion), a single diagnosis for the AE is preferred over reporting each individual symptom.

Clinically significant abnormal laboratory or other examination (e.g., ECG) findings that are detected during the study or are present at the time of screening and significantly worsen during the study are defined and should be reported as adverse events. The Investigator will exercise his or her medical and scientific judgment in deciding whether an abnormal laboratory finding, or other abnormal assessment is clinically significant. Clinically significant abnormal laboratory values occurring during the clinical study will be followed until repeat tests return to normal, stabilize, or are no longer clinically significant. Any abnormal test that is determined to be an error does not require reporting as an adverse event. Laboratory abnormalities will be separately categorized from clinical AEs.

Worsening of the index indication (cryptococcal meningitis) due to insufficient therapeutic effect of study drug is captured as an efficacy measure (i.e., death, poor early fungicidal activity) and in general will not be considered an adverse event but are captured in other individual trial endpoints. As participants enter the trial with Grade 4 cryptococcal meningitis, worsening is not possible, unless death occurs.

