9.2.2 Causality of Adverse Events

The probable causality of the investigational study drug being related to the AE will be collected.

Definitely related	There is a certainty that the AE is related to the study drug.
Probably related	There is a high likelihood that the AE is related to the study drug.
Possibly related	There is a likelihood that the study drug is the cause of the AE, but other causes cannot be ruled out.
Unlikely to be related	It is not likely that the AE is related to the study drug, and other more likely causes are present.
Unrelated	Evidence exists that the AE is related to something other than the study drug.

AEs will use pre-defined causality for the common, expected medical conditions associated with HIV/AIDS (e.g., TB, new opportunistic infections), other infections (e.g., malaria, pneumonia) and cryptococcal meningitis complications. Refer to Manual of Operations for details.

Therapeutic failure of the antifungal therapy alone is not deemed as causal for an AE (i.e. it is unrelated).

The most common disease-related complications and/or standard of care treatment-related side effects include:

- Death due to pre-existing cryptococcosis (up to 20% of enrolled subjects);
- Meningitis complications: e.g., seizures, cranial nerve palsies, increased intracranial pressure
- Transient renal insufficiency in the first 14 days after study entry due to IV amphotericin (20%);
- Cryptococcal IRIS events (~20%);
- AIDS-related opportunistic infections;
- Hospitalization or death due to immune reconstitution inflammatory syndrome (IRIS), cryptococcal culture-positive relapse, or AIDS opportunistic infection (20-25%);^{18,19,26}
- Common ART or flucytosine side effects (e.g., anemia, leukopenia)
- Common IV amphotericin side effects (e.g., anemia, hypokalemia, renal failure)
- Hospital nosocomial infections and other complications (e.g., aspiration pneumonia)

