9.4 Serious Adverse Event

AEs are classified as serious or non-serious. A *Serious adverse event* is:

- fatal
- life-threatening
- requires re-hospitalization (after hospital discharge for the initial, pre-existing meningitis)
- prolonged hospitalization (due to a new AE; not due to pre-existing meningitis or HIV/AIDS)
- results in persistent or significant disability or incapacity
- results in congenital anomaly or birth defect
- an important medical event that may jeopardize the subject or may require immediate intervention to prevent one of the other outcomes listed in the definition above (e.g., anaphylaxis)

All AEs that do not meet any of the criteria for serious will be classified as *non-serious adverse events*. A standard medical problem, e.g., malaria, which in theory if untreated could result in a fatal or life-threatening event, is not by itself a SAE. If the AE is of sufficient severity to result in hospitalization, then the AE is a SAE.

Routine outpatient medical therapy for a common, expected illness in the study population (e.g., malaria, TB) is not a SAE.

All SAEs will be:

- recorded on the appropriate AE CRF
- followed through resolution by a study clinician
- reviewed and evaluated by a study clinician

Important medical events that may not result in death, be life-threatening, or require hospitalization may be considered an SAE when, based upon appropriate medical judgment, they may jeopardize the patient and may require medical or surgical intervention to prevent one of the outcomes listed above. Examples of such medical events include allergic bronchospasm requiring intensive treatment in an emergency room or at home, blood dyscrasias or convulsions that do not result in inpatient hospitalizations, or the development of drug dependency.

Death due to pre-existing cryptococcal meningitis is not a SAE. Death due to a complication of meningitis (e.g., new seizure) would be a SAE.

Prolongation of hospitalization must be due to a new AE, not the pre-existing cryptococcal meningitis or pre-existing HIV/AIDS and related conditions. A *new* AE must cause the prolonged hospitalization for this to be considered a SAE. Hospitalizations due to cryptococcal meningitis commonly may last 2-4 weeks.

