	Thrombocytopenia	4	13	1	3
Infection	Abdominal pain localized	0	1	0	0
	Acinetobacter bacteremia	0	1	0	1
	Acute pneumonia	1	0	0	0
	Bronchopneumonia	1	0	0	0
	Burkholderia cepacia complex	0	1	0	0
	Cystitis, Klebsiella	1	0	1	0
	Disseminated tuberculosis	0	2	0	2
	Klebsiella sepsis	1	1	1	1
	Pulmonary tuberculosis	0	1	0	0
	Salmonella bacteremia	0	1	0	0
	Salmonella sepsis	0	1	0	0
	Sepsis	1	4	1	3
	Septicemia due to pseudomonas	1	1	1	0
	Staphylococcus aureus septicemia	1	0	1	0
	Tuberculosis	0	1	0	1
Neurological	Acute mental status changes	5	3	4	0
	Intracranial pressure increased	3	0	0	0
	Muscle weakness right-sided	2	0	2	0
	Sensory neuropathy	1	0	0	0

Respiratory	Dyspnea	1	1		1	
Dermatological	Erythroderma	1	0		0	
	Rash - morbilliform	0	1		0	
Systemic	HIV wasting syndrome	0	1		0	
	Pyrexia	1	0		0

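### The protocol rules out non-fatal worsening of meningitis yet plans for it elsewhere, so some rescued decompensations can go unrecorded as AEs and take the best DOOR rank

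*Combined protocol and SAP*

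**What the plan says.** Section 9.1 holds two rules. Its general definition counts as an AE any sign or symptom that appears or gets worse on study. Its last paragraph says that worsening of the meningitis through insufficient drug effect "is captured as an efficacy measure (i.e., death, poor early fungicidal activity", that such cases "in general will not be considered an adverse event but are captured in other individual trial endpoints", and that "As participants enter the trial with Grade 4 cryptococcal meningitis, worsening is not possible, unless death occurs".

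Section 9.9 says that symptoms of meningitis are not AEs, that new complications are, and that a pre-existing condition becomes a new AE if it worsens by one grade. Section 9.4 says "Prolongation of hospitalization must be due to a new AE, not the pre-existing cryptococcal meningitis". Section 9.2.2 assigns therapeutic failure to the unrelated category.

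Section 5.5 takes the opposite view of whether worsening can happen: "Examples of progression would be development of altered mental status". It adds a CFU rise of more than 1 log10 as another example, lets low-dose 5-FC be stopped for decompensation, and provides for standard-dose 5-FC afterwards.

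Section 6.2.1.1 says that extra amphotericin will be tracked, "as additional IV AMB is a secondary endpoint". That endpoint appears in neither section 3.2 nor section 11.5.

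**The concern.** The trial lowers a dose, so the harm it most needs to see is treatment failure. Section 9.1 relies on death and poor EFA to show that harm, but a participant who decompensates, is switched and recovers need show neither. DOOR has no rank for decompensation or rescue, so such a participant can rank above one with a Grade 3 hematological AE.

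The comparison with historical controls adds a direction. Trial participants can be moved up to standard-dose 5-FC, whereas the AMBITION controls already received 100 mg/kg/day (section 4.1). If rescued failures are more common on the low dose and are scored as full successes, the low dose looks better than it is. Sites also cannot tell from the text whether to record such an event.

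**Working it through.** No figure in the plan depends on this point, so there is none to reproduce. The check compares the rules, traces one participant, then gives two illustrations on assumed data.

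**1. The rules side by side**

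| Section | Rule | Effect on non-fatal worsening |
|---|---|---|
| 9.1, general definition | A sign that appears or worsens is an AE | AE |
| 9.1, last paragraph | In general not an AE; held to be impossible short of death | No AE |
| 9.9 | Meningitis symptoms are not AEs; new complications are; one-grade rule | From Grade 4 the only step left is 4 + 1 = 5, death; otherwise an AE only if a new complication |
| 9.4 | Stay prolonged by meningitis is not an SAE; life-threatening events, re-hospitalization and lasting disability are | Depends on the event |
| 5.5 | Altered mental status or a CFU rise above 1 log10 is progression | Expected to occur |
| 3.2, 11.5 | DOOR rank a needs 18-week survival and sterility by 2 weeks | Not ranked |

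**2. Trace.** A participant enters with normal mental status, becomes confused in the first admission, stops low-dose 5-FC under 5.5, receives standard-dose 5-FC, is sterile by 2 weeks and is alive at 18 weeks. There is no new complication, re-hospitalization, lasting deficit or Grade 3-4 hematological AE. Reading 9.1 (last paragraph), 9.9 and 9.4 together gives no AE, no SAE and DOOR rank a. Reading the general definition in 9.1 gives an AE. Both readings are open.

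**3. Would EFA show it?** Section 11.1 specifies intent to treat, and no rule covers cultures taken after a switch. The least-squares slope is Σ(d − d̄)(y − ȳ) / Σ(d − d̄)². Assume log10 counts of 5.0, 6.1, 3.5 and 0 on days 1, 3, 7 and 14, so that the count rises by 1.1 before rescue. Then d̄ = 6.25, ȳ = 3.65 and the slope is −43.45 / 98.75 = −0.44 per day. Other assumed profiles with the same early rise give:

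- 5.0, 6.1, 4.5, 0 on the same days: −0.43
- 4.0, 5.1, 3.0, 0 on the same days: −0.36
- 5.0, 6.1, 3.5 on days 1, 3 and 7 only: −0.31

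All are faster than the 0.20 and 0.30 benchmarks that the plan applies to regimens, used here only as yardsticks.

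**4. Scale in DOOR.** The win ratio is P(trial participant ranks better) / P(control ranks better). Three control distributions over ranks a to g were assumed, each with 20% deaths (section 9.2.1 expects up to 20%):

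- A: 0.45, 0.15, 0.08, 0.04, 0.02, 0.06, 0.20
- B: 0.30, 0.20, 0.12, 0.08, 0.02, 0.08, 0.20
- C: 0.55, 0.10, 0.05, 0.03, 0.02, 0.05, 0.20

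The trial arm starts identical to the controls, a share x of it is moved out of rank a, and no control is moved. For A with x = 0.04 (2 of 50) moved to rank b, wins and losses both start at (1 − 0.277)/2 = 0.3615. Wins fall by 0.04 × 0.15 to 0.3555, losses rise by 0.04 × 0.45 to 0.3795, and the win ratio is 0.3555/0.3795 = 0.94.

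| Moved out of rank a | Win ratio, to rank b | Win ratio, to rank f |
|---|---|---|
| 2 of 50 | 0.92-0.95 | 0.89 |
| 5 of 50 | 0.83-0.88 | 0.74-0.75 |
| 10 of 50 | 0.70-0.78 | 0.55-0.58 |

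Rank b is the smallest move. Rank f is shown only to mark the far end of the range.

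**The case against.** The best defence is that the plan catches much non-fatal worsening, and most of that defence stands. The exclusion in 9.1 applies only in general and only to insufficient drug effect. New complications such as seizures are AEs (9.9). Life-threatening events, re-hospitalization and persistent disability are SAEs (9.4), and an SAE puts the participant in DOOR rank f. Section 7.2 lists altered mental status among baseline findings to be recorded so that new AEs can be recognised, which supports calling new confusion an AE. Unrelated does not mean unrecorded, because 9.7 records AEs whatever their relationship to treatment.

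The events also leave a trace. Section 5.5 treats dose alterations as deviations reported to the IRB, 9.8 puts discontinuations on the Med CRF, 11.6 analyses the share of doses received and tolerated, and under 10.3 the DSMB receives tolerability, safety and efficacy reports. A reader might infer that all non-fatal worsening is kept out of the safety data, or that the DSMB cannot see it. The documents support neither inference, and the DSMB Charter and Manual of Operations are not available here.

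What the defence does not remove is the contradiction between 9.1 and 5.5 and within 9.1, or the absence of any stated place for decompensation and switching in the AE listings, DOOR or EFA. A deviation report or a dose percentage does not identify a clinical failure.

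**Conclusion.** The point holds in a limited form. The sections contradict each other, and the fallback in 9.1 fails for a rescued survivor. The gap covers transient worsening in the first admission on the path traced above. Re-hospitalization or a lasting deficit leads to rank f, a culture still positive beyond 2 weeks to rank b, and a new complication to an AE.

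The size is unknown because the plan gives no rate for such cases. The win ratios show scale under assumed distributions with no affected controls; if controls had such events at the same rate, the comparison would shift less or not at all. The slopes rest on assumed counts.

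Two stronger readings fail. A reader might take the 8 events listed in Appendix A as "Acute mental status changes" (5 + 3, among 177 subjects) as an expected rate. That appendix does not attribute them to treatment failure or limit them to 2 weeks, and the trial used amphotericin with fluconazole and randomized ART timing. A reader might also infer that these participants belong in rank f. Nothing in the documents supports placing a recovered, sterile survivor below a Grade 4 hematological event or loss to follow-up, and a switch up from the low dose cannot occur in the controls.

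**What to change.** - Delete or correct the sentence in 9.1, and reconcile 5.5, 9.1, 9.2.2, 9.4 and 9.9 on whether non-fatal decompensation is recorded and how.
- List non-fatal decompensation, any switch from low-dose to standard-dose 5-FC, and any additional amphotericin as reported events regardless of causality. Include the list in the DSMB report.
- Keep DOOR and EFA as planned. Add a sensitivity analysis in which these participants are not counted in rank a and cultures taken after a switch are excluded. For the between-group comparison, use only a definition that can also be applied to the AMBITION controls; report 5-FC switches descriptively for the trial arm.
- Reconcile 6.2.1.1 with 3.2 and 11.5 on whether additional amphotericin is a secondary endpoint.

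The cost is protocol and SAP wording plus one listing and one sensitivity analysis. The Daily Clinical Review Form and Med CRF (sections 9.8 and 13.1) already hold the data. The downsides are that safety and DOOR results may look slightly less favourable, control records may support the definition only in part, and a participant with fewer than two cultures before the switch has no slope in the EFA sensitivity analysis.

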9.2 Assessment of Adverse Events by the Investigator

The Investigator will assess the severity (intensity) of each adverse event as mild, moderate, severe, or life threatening.

9.2.1 Severity of Adverse Events

The term severity is defined as the intensity grade or level for a specific event, i.e., mild, moderate, severe, or life-threatening. Importantly, severity is *not* the same as seriousness, which is based on participant/event *outcome or action* criteria usually associated with events that pose a threat to a subject's life or functioning (ICH E2A). The *Division of AIDS (DAIDS) Table for Grading the Severity of Adult and Pediatric Adverse Events (v2.1, July 2017)* will be used. Laboratory AEs will be defined using the statistical database by DAIDS Table grading thresholds.

The Investigator will assess the severity (intensity) of each adverse event as mild, moderate, severe, or life threatening and will also categorize each adverse event as to its potential relationship to study drug using the categories of yes or no.

Assessment of severity:

The severity of all adverse events should be graded as per The *Division of AIDS (DAIDS) Table for Grading the Severity of Adult and Pediatric Adverse Events (v2.1, July 2017 or*

most current). For those adverse events not listed, the following grading system should be used:

- Mild (Grade 1): Transient symptoms, awareness of sign/symptom, but easily tolerated and no interference with patient's daily activities.
- Moderate (Grade 2): Marked signs/symptoms that interfere with a patient's usual activities, but still acceptable.
- Severe (Grade 3): Incapacitating signs/symptoms which cause considerable interference with the patient's daily activities, unacceptable.
- Life-threatening (Grade 4): Life-threatening or disabling adverse event.
- Death (Grade 5): Death-related adverse event.
 - Death from pre-existing cryptococcal infection is part of the survival endpoint, which is expected to be up to 20% of enrolled subjects. Cryptococcal meningitis deaths without other AEs should not be additionally reported as a Grade 5 AE. The objective is to discern Grade 5 deaths due to adverse events versus deaths from the progression of the pre-existing cryptococcal meningitis. Overall survival will be separately analyzed as the secondary endpoint.

9.2.2 Causality of Adverse Events

The probable causality of the investigational study drug being related to the AE will be collected.

Definitely related	There is a certainty that the AE is related to the study drug.
Probably related	There is a high likelihood that the AE is related to the study drug.
Possibly related	There is a likelihood that the study drug is the cause of the AE, but other causes cannot be ruled out.
Unlikely to be related	It is not likely that the AE is related to the study drug, and other more likely causes are present.
Unrelated	Evidence exists that the AE is related to something other than the study drug.

AEs will use pre-defined causality for the common, expected medical conditions associated with HIV/AIDS (e.g., TB, new opportunistic infections), other infections (e.g., malaria, pneumonia) and cryptococcal meningitis complications. Refer to Manual of Operations for details.

Therapeutic failure of the antifungal therapy alone is not deemed as causal for an AE (i.e. it is unrelated).

The most common disease-related complications and/or standard of care treatment-related side effects include:

- Death due to pre-existing cryptococcosis (up to 20% of enrolled subjects);
- Meningitis complications: e.g., seizures, cranial nerve palsies, increased intracranial pressure
- Transient renal insufficiency in the first 14 days after study entry due to IV amphotericin (20%);
- Cryptococcal IRIS events (~20%);
- AIDS-related opportunistic infections;
- Hospitalization or death due to immune reconstitution inflammatory syndrome (IRIS), cryptococcal culture-positive relapse, or AIDS opportunistic infection (20-25%);^{18,19,26}
- Common ART or flucytosine side effects (e.g., anemia, leukopenia)
- Common IV amphotericin side effects (e.g., anemia, hypokalemia, renal failure)
- Hospital nosocomial infections and other complications (e.g., aspiration pneumonia)

